6.1.3. Blinding

Participants, Investigators, Site staff, CRO staff, and Sponsor staff will remain blinded to treatment assignments except for the designated unblinded Clinical Research Associate (CRA) and the unblinded Medical Monitor.

To avoid potential bias, Investigators and study staff are expected to refrain from sharing safety and treatment outcomes with other participating Sites.

The DSMB, independent of the Sponsor, may review individual unblinded Participant narratives in the case of an SAE or multiple SAEs for which the DSMB Chair requests unblinding, but will not have access to unblinded tables and listings unless requested by the DSMB Chair when assessing a potential safety signal. While the study is ongoing and prior to database lock, the datasets will remain blinded with no preliminary summary of the study by the individual treatment arms except when requested by the DSMB Chair.

6.1.4. Maintenance of the Blind

The treatment assignment for each Participant that was determined by the Interactive Web Response System (IWRS) at randomization in the VMDN-003-2 study will be continued for each Participant in the VMDN-003-2b extension study.

IN CASE OF EMERGENCY (i.e., SERIOUS ADVERSE EVENT [SAE]) AND ONLY WHEN THIS INFORMATION INFLUENCES THE PARTICIPANT'S MEDICAL MANAGEMENT, the Investigator may contact the designated unblinded Medical Monitor to request unblinding of the treatment assignment. The date and reason for unblinding will be documented in the electronic data capture (EDC) system.

6.2. Concomitant Therapy

All concomitant therapies should be captured in the Concomitant Therapy section of the eCRF.

Version 1.0 32 Final: 11 Feb 2021

6.2.1. Rescue Medicine

The only allowed rescue medication is acetaminophen in the VMDN-003-2b extension study. On Day 180 of the VMDN-003-2b extension study, the Site will dispense extra-strength acetaminophen (500 mg) provided by the Sponsor. The Participant will be instructed to take up to 2 caplets every 6 hours as needed for DPN pain for a maximum of 6 caplets (3 grams)/day. The study-issued acetaminophen is only to be used for DPN pain, and the Participant is not to use any other source of acetaminophen for DPN pain. The Participant may use up to 1 gram per day of a source of acetaminophen other than the study-issued Tylenol for conditions other than DPN pain. The Participant will be provided with an eDiary to record their pain level (NRS = 0-10 scale) before use, the date and time of use, and the amount of acetaminophen used. The Participant will be asked to return the eDiary and the unused rescue medication at each Visit. At each Visit, the Site will reconcile how many caplets were used, as documented in the eDiary, with how many caplets remain in the bottle(s). New bottle(s) of acetaminophen will then be dispensed by the Site to the Participant on Days 270 and 300 of this extension study.

6.3. Prohibited and Restricted Medications and Procedures

Prohibited medications and procedures are listed in Section 10.3, Appendix 3.

6.3.1. Medications That May Interfere with Engensis Bioactivity

Certain steroids (except inhaled, ocular, or intra-articular steroids) may interfere with the bioactivity of Engensis and are therefore prohibited from use during the study. Participants must agree to not take any of these drugs for the duration of the VMDN-003-2b extension study. A list of the prohibited medications in this category can be found in Section 10.3, Appendix 3.

6.3.2. Medications and Procedures That May Interfere with Assessment of Pain

Participants must refrain from use of these therapies for the duration of the VMDN-003-2b extension study:

- skeletal muscle relaxants
- opioids
- benzodiazepines (except for stable bedtime dose)
- injectable steroids
- capsaicin applied to the lower legs or feet
- local anesthetic creams and patches applied to the lower legs or feet (except local/topical anesthetic cream applied immediately prior to study drug injections
- ISDN spray applied to the lower legs or feet
- transcutaneous electrical nerve stimulation (TENS), acupuncture

A list of prohibited medications and procedures in this category can be found in Section 10.3, Appendix 3.

If not using a stable dose of duloxetine (Cymbalta), any antidepressants (e.g., amitriptyline and venlafaxine), or any other antiepileptics (e.g., valproic acid, carbamazepine, and vigabatrin)

Version 1.0 33 Final: 11 Feb 2021

during the VMDN-003-2 study, Participants must agree to not start these drugs during the

VMDN-003-2b extension study. Participants on these medications on a stable dose during the VMDN-003-2 study are to continue these medications at the stable dose administered in the VMDN-003-2 study in the VMDN-003-2b extension study. Participants may not use pregabalin (Lyrica) or gabapentin (Neurontin) at any time during the VMDN-003-2b study.

6.4. Prior and Concomitant Medications, Treatments, and Procedures

Medications and treatments recorded at the Day 180 Visit of the VMDN-003-2 study will be migrated to the Medication and History eCRF of the VMDN-003-2b extension study. Any medication or vaccine, including over-the-counter or prescription medicines, vitamins, herbal supplements, and topical anesthetics for post-injection pain and procedures that the Participant is receiving at the time of enrollment or receives during the VMDN-003-2b extension study must be recorded on the Concomitant Medications or Concomitant Procedures eCRF. For each medication or treatment, the following information will be collected:

- · Medication trade or generic name, or procedure
- Indication for which the medication/procedure was given
- Dose/strength, route, and frequency of administration
- Date started and date stopped (or continuation at study exit)
- · Reason for use

The Medical Monitor will be contacted if there are any questions regarding concomitant or prior therapy. Acetaminophen is the only rescue medication allowed in this study. Up to 3 grams per day will be allowed. Use of rescue medication will be recorded each day in the eDiary.

Version 1.0 34 Final: 11 Feb 2021

7. DISCONTINUATION OF STUDY INTERVENTION AND PARTICIPANT DISCONTINUATION

7.1. Participant Discontinuation/Withdrawal/Early Termination from the Study

Any Participant may voluntarily discontinue the VMDN-003-2b extension study at any time without prejudice. The Investigator may discontinue a Participant from the study at any time if, in the Investigator's judgment, the Participant's health or safety would be compromised by remaining in the study.

Specific reasons for study discontinuation include the following:

- · Participant's decision
- Investigator's decision
- Adverse event
- Insufficient compliance with study requirements
- Lost to follow-up
- Other

The specific reasons for Participant discontinuation will be recorded.

The following assessments will be performed, if possible, for Participants who discontinue prior to the VMDN-003-2b extension study Day 365/Early Termination Visit (ET; see Section 1.3, SoA).

- APR and PRR
- Full BPI-DPN
- MNSI
- BST
- PGIC
- SF-36 and EQ-5D
- Complete physical examination
- Vital signs, weight
- Retinal fundoscopy
- Serum chemistry, lipid profile, and hematology
- ECG
- Urine pregnancy test
- Urine drug analysis
- HbA1c
- Concomitant medications / procedures
- Adverse events

Version 1.0 35 Final: 11 Feb 2021

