6. STUDY INTERVENTION

No study drug will be administered to Participants in this VMDN-003-2b extension study.

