8.4.2. Time Period and Frequency for Collecting TEAE and TESAE Information

All TEAEs and TESAEs will be collected from the Day 180 Visit (Study VMDN-003-2) through Day 365/ET of VMDN-003-2b (see definition of TEAE, Section 10.2).

All TESAEs will be recorded and reported to the Sponsor or designee immediately and under no circumstance should this exceed 24 hours, as indicated in Section 10.2.5. The Investigator will submit any updated TESAE data to the Sponsor within 24 hours of its availability.

Investigators are not obligated to actively seek TEAEs or TESAEs after conclusion of the study participation. However, if the Investigator learns of any TESAE, including a death, at any time after a Participant has been discharged from the study, and he/she considers the event to be possibly, probably, or definitely related to the study intervention or study participation, the Investigator must promptly notify the Sponsor.

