10.3 Visit Windows

Data at each scheduled follow-up visit will be analyzed according to the nominal visit identified on the data record.

In case of multiple different visits with the same nominal visit designation, the visit with the visit date closest to the target days of each protocol-specified visit schedule will be used for the efficacy analyses. For visits with the same distance to the target days, the later nominal visit record will be used. Data from all visits will be provided in the data listings.

If a subject fails to complete a study visit but provides necessary eDiary data during the time period expected for that visit (i.e. based on study day relative to the date of the first dose in VMDN-003-2), those eDiary data will be used to derive applicable endpoints. Day 270 endpoint would be derived by the eDiaries recorded 7 days up to 270 days from the date of first dose in VMDN-003-2. Similarly, Day 365 endpoint would be derived by the eDiaries recorded 7 days up to 365 days from the date of first dose in VMDN-003-2. Otherwise, if subject completes study visit, then date of visit will be used to derive applicable endpoints.

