10.6.1 Missing Pain Scores for the Average Scores from BPI-DPN

The means of the Average Daily Pain Scores (Question 5 from the BPI-DPN) for a visit will be considered as missing if fewer than 5 of 7 days of BPI-DPN eDiary entries are provided. Any missing mean pain score of ADPS will be imputed using the methods described below.

Multiple Imputation (MI) method:

- Step 1: Intermittent missing values will first be imputed by treatment group using the Markov Chain Monte Carlo (MCMC) method, resulting in data with a monotone pattern.
- Step 2: Multiple imputation by treatment group using linear mixed model regression with factors of baseline pain score, baseline HbA1c, gender, and age at informed consent (Study VMDN-003-2) will be applied to the data obtained from the MCMC step. The imputed score will be rounded to the first decimal point.

The entire procedure will be repeated 10 times, and 10 complete datasets will be used for the analysis.

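### An early exit from this treatment-free extension ends outcome and safety data collection, and leaves the Day 365 pain score to imputation by arm or possibly to an earlier early-termination score

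*Protocol*

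**What the plan says.** **No treatment.** Protocol Section 6: "No study drug will be administered to Participants in this VMDN-003-2b extension study". The synopsis puts the last injection at Day 104 of the main study.

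**Leaving the study.** In Protocol 7.1 the running text says that the Investigator "may discontinue a Participant from the study at any time if" the participant's health or safety would be compromised by staying. The list below it is wider: it names Investigator's decision, adverse event and "Insufficient compliance with study requirements". The section adds that the reason will be recorded.

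**After leaving.** "The following assessments will be performed, if possible, for Participants who discontinue prior to" the Day 365/ET visit, and the full BPI-DPN is among those assessments. Nothing later is described. The daily diary and adverse event collection run to Day 365/ET (Schedule of Activities, footnotes 12 and 15). Section 8.4.2 adds: "Investigators are not obligated to actively seek TEAEs or TESAEs after conclusion of the study participation". Section 8.4.6 requires events already reported to be followed to resolution or stabilisation.

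**Analysis.** SAP 10.6.1: "Any missing mean pain score of ADPS will be imputed using the methods described below". The method works by treatment group: MCMC for intermittent gaps, then regression on baseline pain, HbA1c, gender and age, giving 10 datasets. SAP 10.3 analyses data by nominal visit and has a diary rule: "If a subject fails to complete a study visit but provides necessary eDiary data during the time period expected for that visit", those diary data are used. SAP 6.1 declines to count an early-termination visit as Day 365, but only for completion status and the PP set.

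**The concern.** In a trial with dosing, stopping treatment and stopping observation are separate decisions. Here only observation can be stopped, so each exit for an adverse event, for compliance or on the Investigator's decision costs data and withdraws no treatment. The losses are the Day 365 primary outcome, the Day 270 outcomes if the exit comes earlier, the remaining fundoscopy, ECG and laboratory assessments, and active detection of new TEAEs and AESIs.

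The stated purpose is durability of efficacy and long-term safety. If people leave for reasons connected with their pain, and the connection or the rate differs by arm, the Day 365 comparison is biased. The secondary endpoints share the exposure: worst pain uses the same missing-data method (SAP 12.5.2.1), and responders are derived from the same imputed datasets (SAP 12.5.2.2).

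**Working it through.** The plan has no figure to reproduce. Neither document states a sample size, effect size, SD, allocation ratio or dropout rate for the extension.

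**Step 1. What happens to the Day 365 score of a participant who leaves early?**
- Route A: the score is missing and is imputed by arm (SAP 10.6.1). The model has no term for discontinuation or its reason. Whether earlier post-baseline scores enter the second imputation step is not stated.
- Route B: an early-termination score is filed under the Schedule of Activities label Day 365/ET and is analysed as that nominal visit (SAP 10.3). SAP 6.1 does not exclude this for the primary analysis.
- Neither route gives the participant's pain at Day 365. The documents do not say which applies.

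**Step 2. Does any planned analysis test this?** SAP 12.5.1.1 repeats the model in the mITT and PP sets. Both require at least 5 of 7 diary days before the Day 365 visit (SAP 9.3, 9.4), so participants without them drop out. The third analysis replaces scores with baseline after prohibited medication used in the 10 days before a visit. None departs from missing at random for those who left.

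**Step 3. Illustrative size under route A. Every input is an assumption.** Let d be the share removed in an arm and g the number of points by which those removed are worse than imputed. Each arm mean is then too low by d × g, so

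error in (Engensis − Placebo) = −(dE·gE − dP·gP), where a negative value favours Engensis.

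| Removed, Engensis v Placebo | g, Engensis v Placebo | Error (points) |
|---|---|---|
| 10% v 10% | 1 v 1, or 2 v 2 | 0 |
| 10% v 5% | 1 v 1 | −(0.10 − 0.05) = −0.05 |
| 10% v 5% | 2 v 2 | −(0.20 − 0.10) = −0.10 |
| 15% v 5% | 2 v 2 | −(0.30 − 0.10) = −0.20 |
| 10% v 10% | 2 v 0 | −(0.20 − 0) = −0.20 |

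Swapping the arms reverses the sign. So does a negative g, which would occur if those who leave go on to get effective pain relief.

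**Step 4. Effect on the two-sided 0.05 test.** With se = SD·√(2/n) and error b, type I error = Φ(−1.96 − b/se) + 1 − Φ(1.96 − b/se). Assume n = 50 to 100 per arm and SD 2.0 to 2.5. At b = −0.10 the result is 0.055 to 0.064; at b = −0.20 it is 0.069 to 0.109. For example, n = 100 and SD 2.0 give se = 2.0 × √0.02 = 0.283, b/se = −0.707 and a type I error of 0.109. This simple two-sample se ignores the gain from repeated measures and the variance added by imputation.

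**Step 5. What continued collection could recover.** If T is the share missing Day 365 and f the part of it due to such removals, full cooperation leaves T × (1 − f). For an assumed T of 10% and f of 25%, 50% or 75%, that is 7.5%, 5.0% or 2.5%. For T = 20% it is 15%, 10% or 5%.

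**The case against.** **The list in 7.1 may only be reason codes.** The running text ties Investigator discontinuation to health or safety, and Section 7.2 tells sites to pursue people who miss visits. This stands as a reading. But the list is introduced as reasons for study discontinuation, and nothing says that data collection continues, so the two parts need reconciling.

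**Removal for using a prohibited pain therapy.** Section 6.3.2 says "Participants must refrain from use of these therapies for the duration of the VMDN-003-2b" extension study, so a reader might infer that someone whose pain drives them to such a therapy is non-compliant and will be removed, which would tie removal to the outcome. The documents do not say so. No section makes such use a ground for discontinuation, and SAP 12.5.1.1 and 12.5.2.3 presuppose that some users stay to have their scores replaced.

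**Imputation from those who stayed.** This too goes further than the text. Imputation is within arm on baseline factors, the participant's own observed visits stay in the repeated-measures model (SAP 12.5.1), and an early-termination score may be used instead.

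**Safety.** Follow-up does not stop altogether. Known events are followed (8.4.6), and related TESAEs learned of later must be notified (8.4.2). What ends is the active search for new events.

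**Direction and size.** Removed participants need not have worse pain than imputed, and nothing in the documents links AESIs such as cancer to the pain score. Protocol 4.3 reports that discontinuation in earlier studies was not unacceptable. These points stand and limit the claim.

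**Conclusion.** The point holds as a design weakness that is cheap to repair. The documents describe no data collection after an early exit from a study that has no treatment to stop. They leave open how an early-termination score enters the primary analysis, and they plan no analysis that relaxes missing at random for people who leave.

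The documents do not show that the result will be biased, or towards which arm. If removal and its link with pain are the same in both arms, the error is zero and only information is lost. The errors of 0.05 to 0.20 points and type I error up to 0.109 rest wholly on assumed removal shares, gaps, sample sizes and SDs. A reader might also take the ITT wording, analysis by assignment regardless of treatment received, as a promise to observe everyone to Day 365. It concerns assigned versus received study drug and does not carry that meaning.

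**What to change.** **Protocol 7.1.** Reconcile the running text with the list. State that non-compliance or an adverse event does not by itself end data collection. Unless consent to data collection is withdrawn, a participant who stops clinic visits, including on the Investigator's safety judgement, keeps the eDiary for Questions 3 and 5 and is contacted by telephone about TEAEs, TESAEs and AESIs at the planned Day 270, 300 and 365 time points. Record stopping visits separately from withdrawing consent to data.

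**SAP 10.3.** The diary rule is written for a missed visit. Extend it explicitly to participants who have stopped visits, so that their in-window Day 270 and Day 365 diary scores enter the ITT analysis as observed. Apply the existing prohibited-medication sensitivity analysis to them. This adds no new estimand, because the primary analysis already takes scores after prohibited medication as observed. State that an early-termination score obtained outside the Day 365 window is not used as Day 365.

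**Cost.** Wording changes to the protocol, consent form and SAP, a few devices kept longer and a few calls. Question 5 gives the ADPS and Question 3 the worst pain score, and both are already in the daily diary, so no new instrument is needed. Some participants will decline, and their scores will still have to be imputed.

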7.2. Lost to Follow-up

A Participant will be considered lost to follow-up if he or she repeatedly fails to return for scheduled Visits and is unable to be contacted by the Site by Day 365/ET (+7 days) in the VMDN-003-2b extension study.

The following actions must be taken if a Participant fails to return to the clinic for a required Study Visit:

- The Site must attempt to contact the Participant and reschedule the missed Visit as soon
 as possible. The Site must counsel the Participant on the importance of maintaining the
 assigned Visit schedule and ascertain whether the Participant wishes to and/or should
 continue in the study.
- If no response is obtained from the Participant, the Investigator is encouraged to contact one of the Participant's relatives or his/her general practitioner.
- Before a Participant is deemed lost to follow-up, the Investigator or designee must make
 every effort to regain contact with the Participant, including at least three telephone calls
 and, finally, a certified letter to the Participant's last known mailing address. These
 contact attempts should be documented in the source records.
- Should the Participant continue to be unreachable, the Participant will be considered lost to follow-up.

Version 1.0 36 Final: 11 Feb 2021

8. STUDY ASSESSMENTS AND PROCEDURES

Study procedures and their timing are summarized in Section 1.3 (SoA).

Protocol waivers or exemptions are not allowed. Adherence to the protocol requirements, including those specified in the SoA, is essential.

8.1. Participant Training

8.1.1. Accurate Pain Reporting

The Accurate Pain Reporting (APR) training instructs Participants how to report pain scores accurately and reliably, and on the proper use of pain scales, with the aim of increasing the reporting accuracy of Participant pain. Participants will receive training on Days 270, 300, and 365/ET.

8.1.2. Placebo Response Reduction

The Placebo Response Reduction (PRR) training teaches the Participant about the appropriate expectations of personal benefit while participating in a clinical trial. The purpose is to provide Participants with truthful information that will neutralize the typically excessive expectations that drive high placebo responses in clinical studies. Participants will receive training on Days 270, 300, and 365/ET.

8.2. Efficacy Assessments and Procedures

8.2.1. Brief Pain Inventory for Diabetic Painful Neuropathy

The Brief Pain Inventory for Diabetic Painful Neuropathy (BPI-DPN) assessment tool (Section 10.5, Appendix 5) will be administered through use of an eDiary. The Investigator should ensure that the Participant is provided with instructions and is trained to use the eDiary and to complete the assessment tool properly before data collection begins. The BPI-DPN will be conducted using the Full BPI-DPN questionnaire and the Partial BPI-DPN questionnaire

Scores obtained from the Full BPI-DPN during the 7 days prior to the Day 270 and Day 365/ET Visits will be used to determine ADPSs. The ADPS is the mean of at least 5 daily pain scores recorded in the eDiary. If the eDiary contains fewer than 5 daily entries over the 7 days prior to the Day 270 or the Day 365/ET Visits, the Visit must be rescheduled so that the Participant can record 5 daily entries over the 7 days prior to the rescheduled Visit.

Participants will use the eDiary to rate their Average Daily Pain and Worst Daily Pain included in the Brief BPI-DPN on a daily basis from the Day 180 Visit (Study VMDN-003-2) to the Day 365/ET Visit of this extension study to allow an assessment of the level and duration of pain relief in the active treatment group versus Placebo.

Version 1.0 37 Final: 11 Feb 2021

8.2.2. Quality of Life/Participant Reported Outcome Measures

8.2.2.1. Patient Global Impression of Change

The Participant's impression of change after treatment will be measured with the Patient Global Impression of Change (PGIC) questionnaire through use of an eDiary. The Investigator should ensure that the Participant is provided with instructions and is trained to use the eDiary and to complete the assessment tool properly before data collection begins (Section 10.6, Appendix 6). This questionnaire measures the Participant's perception of how treatment has affected their level of activity, symptoms, emotions, and overall quality of life. Each descriptor is ranked on an intensity scale of 1 = Very Much Improved; 2 = Much Improved; 3 = Minimally Improved; 4 = No Change; 5 = Minimally Worse; 6 = Much Worse; 7 = Very Much Worse. The test will be self-administered during the Day 270 and Day 365/ET Visits.

Upon completion of the questionnaire, the study coordinator will check the questionnaire for completeness. Any omissions or ambiguous answers will be clarified by the Participant prior to leaving the clinic.

